### **2.1.1.10 Change from baseline**

Change from baseline will be calculated as:

$$(\text{Post-baseline value} - \text{baseline value})$$

Change from baseline will only be calculated and summarized for participants with both baseline and post-baseline values.

### **2.1.1.11 Discontinuation from study treatment**

Discontinuation of study drug for a participant occurs when study drug is permanently stopped for any reason (prior to the planned completion of study drug administration, if any), and can be initiated by either the participant or the Investigator.

### **2.1.1.12 Discontinuation from study**

Discontinuation from study for a participant occurs when they permanently stop receiving the study treatment, and further protocol-required assessments or follow-up, for any reason.

## **2.2 Analysis sets**

### **Full analysis set**

The Full Analysis Set (FAS) comprises all participants who have received at least one dose of the investigational drug.

### **Safety set**

The Safety Set (SAF) is identical to the FAS in this study.

### **2.2.1 Subgroup of interest**

There is no subgroup analysis planned for this study.

## **2.3 Patient disposition, demographics and other baseline characteristics**

Unless stated otherwise, all patient disposition, demographics, medical history and baseline characteristics data will be listed and summarized descriptively for the FAS.

### **2.3.1 Patient disposition**

Participant disposition will be summarized for the following study periods: screening, baseline, study and 30 day Telephone follow-up.

Patient disposition for each period will be summarized for all participants who entered that period. Participants who have entered any study period but have discontinued from the study will be listed as appropriate along with the primary reason for discontinuation.

The number and percentage of screening failures and the reason for screening failure will be presented for all screened participants.

For each protocol deviation, the number and percentage of participants for whom the deviation applies will be tabulated.

### **2.3.2 Demographics**

The following demographic variables will be listed and summarized descriptively:

#### **Continuous variables**

- Age (years)
- Height (cm)
- Weight (kg)
- Body mass index (BMI) ( $\text{kg}/\text{m}^2$ ) = (weight in kg)/(height in meters)

Weight and height will be reported as captured in the “Vital signs” eCRF page at baseline. If there is no weight recorded prior to taking of study treatment, BMI will be missing.

#### **Categorical variables**

- Sex (Male, female, unknown, undifferentiated)
- Ethnicity (Hispanic or Latino, not Hispanic or Latino, not reported, unknown)
- Race (White, Black or African American, Asian (Chinese, Indian, Japanese, Korean, Vietnamese), Native Hawaiian or Pacific Islander, American Indian or Alaska Native, Multiple)

### **2.3.3 Baseline characteristics**

Baseline disease characteristics will be summarized for the following variables:

- **MS baseline characteristics:**

- [REDACTED]
- Baseline lymphocyte value, including reporting of lymphocyte abnormalities (CTCAE grade).
- [REDACTED] Immunoglobulin G (IgG) and Immunoglobulin M (IgM) value.
- MRI parameters including:
  - Number of GdE enhancing T1 lesions
  - Number of GdE enhancing T1 upper cervical cord lesions

[REDACTED]

**• MS disease history:**

- Duration of Multiple Sclerosis (MS) since diagnosis (years) defined as: (first study treatment administration date – date of MS diagnosis + 1)/365.25
- Duration of MS since first symptom (years) defined as: (first study treatment administration date – first MS symptom date + 1)/365.25
- Number of relapses in the last 12 months prior to screening
- Number of relapses in the 12 to 24 months prior to screening
- Type of MS at study entry (Relapsing-remitting MS (RRMS), Secondary progressive MS (SPMS))
- Time since onset of most recent relapse (months) prior to screening defined as: (first study treatment administration date – most recent relapse onset date + 1)/(365.25/12)
- **Participants' employment status** (part-time, full-time, not employed)

**2.3.4 Medical history**

Relevant medical histories and current medical conditions at baseline (i.e., prior to the first dose of the study treatment) will be summarized by system organ class (SOC) and preferred term (PT) for the SAF.

Medical histories will be coded using the Medical Dictionary for Regulatory Activities (MedDRA) terminology. The latest version of which (at the time of the data cut-off) will be used for the reporting activity.

**2.4 Treatments (study treatment, rescue medication, prior and concomitant therapies, compliance)**

Unless otherwise stated, the SAF will be used for all treatment summaries.

**2.4.1 Study treatment / compliance**

**Exposure to study treatment**

Duration of exposure to the study treatment will be calculated as

$$(\text{date of last administration of study drug} - \text{date of first administration of study drug} + 1 + 30.4375 - \sum [(\text{j} + 1)^{\text{th}} \text{ administration date} - \text{j}^{\text{th}} \text{ administration date} - 33.4375]).$$

Where j and j + 1 refer to consecutive study drug administration dates more than 33.4375 days apart (as participants are scheduled to receive the study drug once monthly  $\pm$  3 days).

The duration of exposure will include any periods of temporary dose interruption.

Duration of exposure to the study drug will be summarized by duration category (i.e.,  $\geq 1$  week,  $\geq 2$  weeks,  $\geq 3$  weeks,  $\geq 4$  weeks,  $\geq 8$  weeks,  $\geq 12$  weeks,  $\geq 24$  weeks,  $\geq 36$  weeks, and  $\geq 48$  weeks,  $\geq 52$  weeks).

A listing of the drug doses administered will be provided.

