Visit Window Days (d)			±1d	±1d	±3d	±3d	±3d	±3d	±3d	±3d	±3d	±3d	±3d	±3d	±3d	±3d	±7d	
Self-injection Training (Participant and/or caregiver)		S																
Study drug self-injection (at Home) ⁸			X	X		X	X	X	X		X	X	X	X	X			
Administration of study treatment at site ²²		X			X					X						X		
Drug Accountability		S			S					S						S		
Dispensation of study drug 2,4, 7,12,13,14		S 2,4, 7 12,13			S ¹⁴					S ¹⁴						S ¹⁴		S ¹⁴
Dosage Administration Record		X			X					X						X		
Concomitant Medications ⁸	X	X ¹²	X	X	X	X	X	X	X	X	X	X	X	X	X	X	X	X
Adverse Events/ Serious Adverse Events ⁸	X	X ¹²	X	X	X	X	X	X	X	X	X	X	X	X	X	X	X	X
C-SSRS	X ¹²				X					X						X		X

Period ¹	Screening / BSL		Treatment Period													End of Treatment /Study	Follow-up	Unplanned
Visit Name	Screening	BSL V1	V2	V3	V4	V5	V6	V7	V8	V9	V10	V11	V12	V13	V14	EOT/EOS V15 ⁵	Safety	Unscheduled Visit
Visit Day (D)/Month (M)	-28 Days	D1	D7	D14	M1	M2	M3	M4	M5	M6	M7	M8	M9	M10	M11	M12	30-Day Tel.	UPV
Visit Window Days (d)			±1d	±1d	±3d	±3d	±3d	±3d	±3d	±3d	±3d	±3d	±3d	±3d	±3d	±3d	±7d	
TSQM-9 ¹³		X ¹²			X					X						X		X
Thank You Letter		S														S		
Health Status Telephone Call ⁸			S ⁸	S ⁸		S ⁸	S ⁸	S ⁸	S ⁸		S ⁸	S ⁸	S ⁸	S ⁸	S ⁸		S ⁸	

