16.3.4 Guidance on monitoring of Participants with low immunoglobulin levels

During the study, the immunoglobulin levels (IgG and IgM) will be measured according to the schedule in [Table 8-1](#) and [Table 8-2](#). If IgG levels were to drop below 300mg/dL ([Agarwal and Cunningham-Rundles 2007](#)), study drug treatment should be interrupted and the Investigator should evaluate participant for any potential infections and monitor on a regular basis. Immunoglobulin substitution therapy as per local medical practice is allowed. In case of treatment interruption, re-initiation of the study drug can only be considered once the immunoglobulin levels are back within normal limits.

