#### **2.1.1.6 On-treatment period (efficacy analyses)**

The on-treatment period for efficacy analyses is defined as:

$$(\text{Last study treatment administration date} - \text{first study treatment administration date}) + 31.4375$$

The on-treatment period definition applies to efficacy analyses only. This definition considers that participants are scheduled to administer the study drug once monthly.

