## **Treatment compliance**

Compliance to the study drug administration schedule will be calculated as:

(Duration of exposure to study drug in (days)/duration of on-treatment period in (days)) × 100%

This rule means that compliance will be measured during the time interval the participant took study drug: premature discontinuation from study drug will not be considered non-compliance. Compliance to study drug administration will be summarized descriptively for the SAF. In addition, compliance will be summarized with cumulative number and percentage of participants in each compliance category (i.e.,  $\geq 20\%$ ,  $\geq 30\%$ ,  $\geq 40\%$ ,  $\geq 50\%$ ,  $\geq 60\%$ ,  $\geq 70\%$ ,  $\geq 80\%$ ,  $\geq 90\%$ ,  $\geq 95\%$ ,  $\geq 98\%$ , =100%).

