### **2.4.2 Visit windows**

Visit windows will be used for the data that is summarized by visit; they are based on the study evaluation schedule and comprise a set of days around the nominal visit day. For any assessment, there are the protocol defined scheduled visits around which visit windows are created to cover the complete range of days within the study.

The visit windows for the on-treatment period are shown in [Table 2-1](#). In this table, the days are counted since the first dose of study treatment (study days) for safety and efficacy assessments. These windows apply to measurements taken at every visit. For assessments collected less often different visit windows will be applied as detailed below. Similarly, visit windows for the post-treatment safety follow-up period are shown in [Table 2-2](#). Unless specified otherwise these windows will be applied for all assessments.

When visit windows are used, all visits will be re-aligned, i.e., they will be mapped into one of the visit windows. E.g., if the Visit 4 visit of a participant is delayed and occurs on Day 62 instead of on Day 30, say, it will be re-aligned to visit window Visit 5. In the case of major deviations from the visit schedule, or due to unscheduled visits, several assessments of a participant may fall in a particular visit window (either scheduled or unscheduled). Statistical approaches to handle multiple assessments in a given visit window are specified below.

Tables displaying summary statistics “by visit” will also use the term visit-window as column header; this is to remind the reviewer that multiple assessments of a patient might be summarized.

As a rule, the following steps are followed to determine the cut-offs for post-baseline time windows:

- Transform all scheduled assessment time points into study days, assuming 1 month is equal to 30.4375 days. Middle points of scheduled assessments are determined.
- The time window associated with the previous assessment ends prior to the middle point; the time window associated with the latter assessment begins after the middle point. In case the middle point is an exact study day, it will belong to the previous assessment.
- The time window of first post-baseline assessment starts with Study Day 2, unless otherwise indicated.

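### SAP 2.4.1 prints an exposure formula that deducts long dose gaps and then says that interruptions count as exposure; with the 2.1.1.6 denominator, the second rule makes compliance 100% for everyone

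*SAP*

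**What the plan says.** SAP 2.4.1, under the exposure subheading, gives an explicit formula: last dose date minus first dose date, plus 1, plus 30.4375, minus a sum over dose gaps. The sum runs over "consecutive study drug administration dates more than 33.4375 days apart", and each such gap contributes its length minus 33.4375. That threshold is one month (365.25/12 = 30.4375 days) plus the 3-day dosing window.

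After the formula comes the sentence "The duration of exposure will include any periods of temporary dose interruption".

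The quantity is used twice in 2.4.1. It feeds the exposure-duration categories (from at least 1 week to at least 52 weeks). It is also the numerator of compliance, defined as "Duration of exposure to study drug in (days)/duration of on-treatment period in (days" (closing brackets omitted) times 100%. Compliance is tabulated for the Safety Set in rows from at least 20% up to exactly 100%. The same section says that compliance covers the interval in which drug was taken and that early stopping is not non-compliance.

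SAP 2.1.1.6 sets the on-treatment period at last minus first dose plus 31.4375 and adds: "The on-treatment period definition applies to efficacy analyses only". Protocol 12.3 says only that exposure is summarized descriptively, and SAP Table 4-1 lists no changes to protocol-specified analyses.

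**The concern.** The formula keeps at most 33.4375 days of any gap, while the sentence keeps all of it. They agree only when the gap is no more than 3 days over a month, and that is ordinary dosing within the window. For a real interruption the programmer has to choose.

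Interruptions are foreseen. Protocol 6.5.3 allows them at the investigator's judgement. Protocol 16.3.4 calls for one when IgG falls below 300 mg/dL, and then "re-initiation of the study drug can only be considered once the immunoglobulin levels are back within normal limits". SAP 2.8.1 plans a separate summary of adverse events leading to interruption.

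Two tables are at stake: which exposure rows an interrupted participant reaches, and whether the compliance table can show anything other than 100%. The denominator adds a second uncertainty. Compliance is a Safety Set summary, yet the only on-treatment formula in the SAP is reserved for efficacy analyses.

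**Working it through.** The documents state no compliance figure to reproduce, so the printed rules are evaluated directly.

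**Inputs**
- Month length: SAP 2.4.2, "assuming 1 month is equal to 30.4375 days".
- Dose days: Days 1, 7 and 14 (Protocol 6.3.2), then the SAP Table 2-1 visit days for Months 1 to 12: 31, 62, 92, 123, 153, 184, 214, 245, 275, 305, 336, 366.
- Last dose: Day 336 (Month 11), or Day 366 (Month 12), because Protocol Table 8-1 also marks the row "Administration of study treatment at site" at Month 12.
- Denominator: SAP 2.1.1.6, assumed to apply to compliance.

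**Formulas**
- On-treatment period: T = last − first + 31.4375.
- Exposure under the formula: last − first + 1 + 30.4375 − Σ(gap − 33.4375), over gaps longer than 33.4375.
- Exposure under the sentence (no deduction): last − first + 1 + 30.4375 = last − first + 31.4375.

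**Step 1, the identity.** The last expression equals T. Under the sentence, compliance is therefore T/T = 100% for any dosing pattern.

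**Step 2, the two denominators.** Last dose Day 336: 335 + 31.4375 = 366.4375 days (52.35 weeks). Last dose Day 366: 365 + 31.4375 = 396.4375 days (56.63 weeks). With no dose skipped the longest gap is 31 days, nothing is deducted, and both rules give 100%.

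**Step 3, deductions under the formula.** Month 3 skipped: 123 − 62 − 33.4375 = 27.5625. Months 3 to 5 skipped: 184 − 62 − 33.4375 = 88.5625.

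| Skipped | Last dose | Exposure, formula | Compliance, formula | Exposure, sentence | Compliance, sentence |
|---|---|---|---|---|---|
| Month 3 | Month 11 | 338.875 d (48.41 wk) | 92.5% | 366.4375 d | 100% |
| Months 3–5 | Month 11 | 277.875 d (39.70 wk) | 75.8% | 366.4375 d | 100% |
| Month 3 | Month 12 | 368.875 d (52.70 wk) | 93.0% | 396.4375 d | 100% |
| Months 3–5 | Month 12 | 307.875 d (43.98 wk) | 77.7% | 396.4375 d | 100% |

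With a Month 11 last dose, one skip takes the participant out of the 52-week row. Three skips also take the participant out of the 48-week row and the 80% compliance row.

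**Step 4, how general the three-skip figures are.** All sets of three skipped monthly doses with a later dose were enumerated, for both last-dose days.
- Lowest: 75.8%, for example Months 2–4 or 3–5 with the last dose at Month 11.
- Highest: 82.7%, Months 1, 9 and 11 with the last dose at Month 12. The deductions are (62 − 14 − 33.4375) + (305 − 245 − 33.4375) + (366 − 305 − 33.4375) = 14.5625 + 26.5625 + 27.5625 = 68.6875, and 327.75/396.4375 = 82.7%.
- Skipping Month 1 costs less because the Day 14 to Month 2 gap is shorter. Months 1–3 skipped with a Month 12 last dose: 123 − 14 − 33.4375 = 75.5625, and 320.875/396.4375 = 80.9%.

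**Step 5, a late dose.** Month 3 dose given on Day 102, others on schedule, last dose Day 336: the gap is 40 days and the deduction 6.5625, so exposure is 359.875 days (51.41 weeks) and compliance 98.2%.

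**The case against.** **A programmer would probably use the formula.** The SAP presents the formula as how exposure is calculated and defines its terms, and graded compliance rows make sense only with a deduction. This stands as a statement of likelihood. It does not remove the conflict, because the sentence is equally explicit and nothing ranks the two.

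**The sentence may be what was meant for the exposure-duration table.** The 100% argument supports the formula only as the compliance numerator, and Protocol 12.3 is silent. That is fair. But the formula is printed as the definition of exposure itself, so keeping it follows the SAP's own text, and the other quantity can be reported separately.

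**Skipped doses are not the default.** Protocol 6.7.2 says that a missed monthly injection should be given as soon as possible, and Step 5 shows how little a 10-day delay does to compliance. Scheduled post-baseline IgG tests fall at Months 1, 6 and 12, so the IgG rule does not naturally produce a Months 3 to 5 gap, although unscheduled tests could. Both points stand. The examples are illustrations, and the documents give no count of interruptions.

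**Stronger readings that a reader might infer.** One is that three skipped doses always fall below 80%. They do not: patterns that include Month 1 can stay above it, and doses missed just before a permanent stop are not deducted at all, which follows from the SAP's stated rule on early stopping. Another is that reported compliance will be 100% for everyone. That needs both the sentence to be followed and the 2.1.1.6 denominator, and Protocol 12.5.2 describes a longer on-treatment period for safety analyses. The description in 2.4.1 of the interval in which drug was taken favours 2.1.1.6, but the SAP does not say so.

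**Conclusion.** The contradiction is real and legible, and one of the two rules has to go. Given the 2.1.1.6 denominator, the sentence makes compliance exactly 100% by algebra. Under the formula, three consecutive skips at Months 3 to 5 cost 24.2 percentage points (100 − 75.8) or 22.3 points (100 − 77.7), and any three skips with a later dose cost about 17.3 to 24.2 points. These figures rest on nominal visit days and on that denominator. With about 100 participants, each interrupted participant moves an affected row by about one percentage point.

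The practical weight is small. Only the descriptive exposure and compliance tables are involved. The documents do not support extending the point to the primary endpoint, to retention (based on drug discontinuations) or to the sample size, because none of them uses this exposure quantity. It is a low-priority correction worth making because it costs almost nothing.

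**What to change.** In SAP 2.4.1:

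1. Delete the sentence about temporary interruptions and keep the printed formula as the single definition of exposure, for both the duration and the compliance tables.
2. State there that the compliance denominator is last dose date minus first dose date plus 31.4375 days, for all participants and whatever the reason for stopping. This settles the efficacy-only label in 2.1.1.6.
3. If elapsed time including interruptions is also of interest, report that denominator as a separate, separately named summary.

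The cost is one deleted sentence and one added line in the SAP before database lock. It needs no new data, no new derivation and no protocol amendment.

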## **Treatment compliance**

Compliance to the study drug administration schedule will be calculated as:

(Duration of exposure to study drug in (days)/duration of on-treatment period in (days)) × 100%

This rule means that compliance will be measured during the time interval the participant took study drug: premature discontinuation from study drug will not be considered non-compliance. Compliance to study drug administration will be summarized descriptively for the SAF. In addition, compliance will be summarized with cumulative number and percentage of participants in each compliance category (i.e.,  $\geq 20\%$ ,  $\geq 30\%$ ,  $\geq 40\%$ ,  $\geq 50\%$ ,  $\geq 60\%$ ,  $\geq 70\%$ ,  $\geq 80\%$ ,  $\geq 90\%$ ,  $\geq 95\%$ ,  $\geq 98\%$ , =100%).

### **2.4.2 Visit windows**

Visit windows will be used for the data that is summarized by visit; they are based on the study evaluation schedule and comprise a set of days around the nominal visit day. For any assessment, there are the protocol defined scheduled visits around which visit windows are created to cover the complete range of days within the study.

The visit windows for the on-treatment period are shown in [Table 2-1](#). In this table, the days are counted since the first dose of study treatment (study days) for safety and efficacy assessments. These windows apply to measurements taken at every visit. For assessments collected less often different visit windows will be applied as detailed below. Similarly, visit windows for the post-treatment safety follow-up period are shown in [Table 2-2](#). Unless specified otherwise these windows will be applied for all assessments.

When visit windows are used, all visits will be re-aligned, i.e., they will be mapped into one of the visit windows. E.g., if the Visit 4 visit of a participant is delayed and occurs on Day 62 instead of on Day 30, say, it will be re-aligned to visit window Visit 5. In the case of major deviations from the visit schedule, or due to unscheduled visits, several assessments of a participant may fall in a particular visit window (either scheduled or unscheduled). Statistical approaches to handle multiple assessments in a given visit window are specified below.

Tables displaying summary statistics “by visit” will also use the term visit-window as column header; this is to remind the reviewer that multiple assessments of a patient might be summarized.

As a rule, the following steps are followed to determine the cut-offs for post-baseline time windows:

- Transform all scheduled assessment time points into study days, assuming 1 month is equal to 30.4375 days. Middle points of scheduled assessments are determined.
- The time window associated with the previous assessment ends prior to the middle point; the time window associated with the latter assessment begins after the middle point. In case the middle point is an exact study day, it will belong to the previous assessment.
- The time window of first post-baseline assessment starts with Study Day 2, unless otherwise indicated.

- For parameters, which are not collected at every visit, visit windows will be combined. For example, if a parameter is measured at Month 2 and Month 12 only, Month 2 visit window will extend from Month 2 to Month 12 (combining Month 2 and Month 12 visit windows).

**Table 2-1 Visit windows for the on-treatment period**

Analysis visit	Time point	Scheduled visit day (study days)	Visit window (study days)
Baseline	Day 1	1	-28 to 1*
Visit 2	Day 7	7	2 to 10
Visit 3	Day 14	14	11 to 22
Visit 4	Month 1	31	23 to 46
Visit 5	Month 2	62	47 to 77
Visit 6	Month 3	92	78 to 107
Visit 7	Month 4	123	108 to 138
Visit 8	Month 5	153	139 to 168
Visit 9	Month 6	184	169 to 199
Visit 10	Month 7	214	200 to 229
Visit 11	Month 8	245	230 to 260
Visit 12	Month 9	275	261 to 290
Visit 13	Month 10	305	291 to 320
Visit 14	Month 11	336	321 to 351
EOS (Visit 15)	Month 12	366	352 to 381
30-day tel. safety FU	Month 13	396	382 to 427

\*Baseline measurement before the first study drug administration for safety and efficacy assessments.

